#### **11.5 DATA SOURCES**

The study will mainly involve new data collection, by means of a web based data capture (WBDC) system. Data will be collected by the study physicians as generated according to the standard clinical practice and by the patients as captured with the use of PROs. No further laboratory tests and examinations are required apart from those recommended by the study medication SmPC.

Patient source data pertaining to medical- and lung cancer-related history will be abstracted from patient medical charts/records by the investigators and will be recorded in the relevant section of the WBDC.

All afatinib treatment modifications, concomitant medications, study-related routine clinical assessments, adverse events (AEs) and vital status will also be collected. Regarding vital status, if a patient is prematurely withdrawn from the study, he/she will be contacted by telephone or other methods to assess vital status at the end of study unless the patient has actively withdrawn consent for all forms of contact (refer to section [11.2.4.3](#)).

Concomitant or prior disease-related medications entered into the database will be coded using the Anatomical Therapeutic Chemical (ATC) WHO Collaborating Centre for Drug Statistics Methodology (WHOCC) Drug Reference List.

Medical history/comorbidities and adverse events will be coded using Medical Dictionary for Regulatory Activities (MedDRA) terminology.

In addition, physicians will be requested to assess:

- **Patients' performance status** using the ECOG PS instrument. (*For a sample of the English version please refer to [ANNEX 3: ECOG PERFORMANCE STATUS SCALE](#)*).

Furthermore, the **following PROs** will be collected via self-administered paper questionnaires completed by the patients themselves at study enrolment and periodically throughout study participation, according to the study visit frequency.

- **Disease-specific symptoms** will be measured using the self-administered patient-rated LCSS, a reliable and valid lung cancer-specific instrument that is comprised of two components, the patient-rated scale employed in the present study and the observer-rated [\[20, 36, 37\]](#).

The patient-rated LCSS questionnaire consists of nine items, each scored with a 100-mm VAS used to evaluate six symptoms associated with lung cancer (loss of appetite, fatigue, cough, dyspnea, pain, and hemoptysis) as well as three global items used to evaluate the interference with normal activities, distress from lung cancer symptoms, and overall QoL. The mean of the 6 major lung cancer symptoms comprises the ASBI that reflects the primary outcome variable in this study. In addition, the LCSS total score defined as the mean of the 9 items of the scale will be determined.

The time for LCSS patient scale completion is 8 minutes initially for demonstration of the VAS and 3-5 minutes for subsequent administrations.

*Rationale for selecting LCSS:* The LCSS has been selected as the main PRO in this study since it is focused on symptom burden which is the main objective of the study as well as is more patient-friendly, less time-consuming and provides less patient and staff burden (it comprises 9 items in total compared to the 43 items of EORTC\_LC13) and thus is considered more suitable for use in the common clinical setting in the context of a NIS. In addition, it has demonstrated a good reliability and validity compared to the other PROs [\[10\]](#). (*For a sample of the English version please refer to [ANNEX 3: LCSS PATIENT SCALE](#)*).

- **HRQoL:** The Greek version of Euroqol EQ-5D-3L [38] will be used in order to measure patients' HRQoL at the specific timepoints of the study.

The EQ-5D-3L is a standardized disease-generic instrument for the measurement QoL that has been widely used in both general and specific disease populations. It is cognitively not demanding, taking only a few minutes to complete. It consists of the EQ-5D descriptive system and the EQ VAS. EQ-5D is designed for self-completion by respondents and is ideally suited for use in clinics, and in face-to-face interviews. The EQ-5D-3L descriptive system comprises the following 5 dimensions: mobility, self-care, usual activities, pain/discomfort and anxiety/depression. Each dimension has 3 levels: no problems, some problems, extreme problems.

The EQ VAS records the respondent's self-rated health on a vertical, visual analogue graduated (0–100) scale [17, 39]. *(For a sample of the English version please refer to ANNEX 3: EQ-5D-3L).*

- **Adherence to therapy with afatinib:** A patient diary will be used which the patient will be requested to fill in only with the date and reasons for missed pills. The diary will contain both predefined reasons and free text fields.  
Patient diary is among the accepted methods for estimating treatment adherence. This method has been selected as the less burdensome for the patient (compared with any compliance-specific PRO) and the most accurate in terms of avoiding recall biases [40].

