Data sources:	
The study will mainly involve new data collection, by means of a web based data capture (WBDC) system. Data will be collected by the study physicians as generated according to the standard clinical practice and by the patients as captured with the use of PROs. No further laboratory tests and examinations are required apart from those recommended by the study medication SmPC.
 
Patient source data pertaining to medical- and lung cancer-related history will be abstracted from patient medical charts/records by the investigators and will be recorded in the relevant section of the WBDC.
 
All afatinib treatment modifications, concomitant medications, study-related routine clinical assessments, vital signs and adverse events (AEs) will also be collected.
 
Concomitant or prior disease-related medications entered into the database will be coded using the Anatomical Therapeutic Chemical (ATC) WHO Collaborating Centre for Drug Statistics Methodology (WHOCC) Drug Reference List.
 
Medical history/comorbidities and adverse events will be coded using Medical Dictionary for Regulatory Activities (MedDRA) terminology.
 
PROs (LCSS patient scale and EQ-5D-3L) will be collected via self-administered paper questionnaires completed by the patients themselves at study enrolment and periodically throughout study participation, according to the study visit frequency.
 
For the measurement of the adherence to therapy, a patient diary will be used which the patient will be requested to fill in only with the date and reasons for missed pills.
 
In addition, physicians will be requested to assess the patients' performance status using the ECOG PS instrument.

Study size:	Sample size calculation has been based on study's primary endpoint, which involves the determination of the proportion of study population

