### **10.2 SECONDARY OBJECTIVES**

- To evaluate the effect of afatinib therapy on the patient-reported lung cancer-specific symptom burden, total symptomatic distress, functional activity status and global quality of life, using the LCSS total score and domain subscores, at the post-baseline predefined timepoints (*please refer to Section 11.1.2, for the definition of the post baseline timepoints*);
- To assess the impact of afatinib treatment on the HRQoL of the study population using the EQ-5D-3L questionnaire at the post baseline predefined timepoints;
- To assess the impact of afatinib therapy on patient's ECOG PS at the post baseline predefined timepoints;
- To record patient adherence to treatment with afatinib during the study observation period as well as the reasons for missing doses;
- To assess the patterns of use of afatinib in routine clinical practice in terms of treatment modifications (permanent discontinuations, temporary interruptions, dose changes), and reasons for these modifications.

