### **11.8.2 Analysis for the primary endpoint**

Pertaining to the primary endpoint the proportion of patients experiencing a minimum clinically important symptom improvement (*as defined in Section 11.1.3.1*) over a 6-month period of treatment will be calculated along with the respective 95% confidence interval; in addition the relevant proportions of patients whose symptom burden has remained stable and deteriorated will be calculated. The 95% confidence interval will be derived from Wald confidence limits for a binomial proportion.

In order to examine the impact of baseline characteristics including among others, gender, age, BMI, educational/marital/employment status, disease stage, histological subtype, sites of metastases, EGFR mutation subtype, smoking status and smoking history, ECOG PS, type of concomitant medications and comorbidities, as well as adherence to therapy at 6 months on the study primary endpoint, a binary logistic regression model will be applied.

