#### **11.9      QUALITY CONTROL**

Proper quality control mechanisms and processes will be implemented in order to ensure data quality and integrity through the conduct of the study. All these procedures will be detailed in the study specific DMP and SAP.

The query management process for the eCRF-collected data will be handled on a real-time-basis through built-in edit and logic checks (validation rules) in the eCRF application. If any discrepancies (other than those predicted by the built-in validation

rules) arise before eCRF lock during source data verification (SDV) process (performed by the project monitor) or data review by the Data Manager, queries will be handled electronically through specific application's query functionality, whereas for discrepancies that may emerge after eCRF application lock, paper Data Clarification Forms (pDCF) will be issued manually, using Microsoft Word. For PRO-collected data no queries will be issued. After all data have been properly validated, the quality control procedure has been completed and database lock has been declared, the extracted file will be transferred to sponsor. Statistical analysis performance & CSR development will be performed by a designated CRO.

Statistical programming performed to generate the results as well as all-related documents and forms will be archived electronically.

e-CRF archivals for each participating site will be prepared in CD-ROMs by the designated CRO, upon study completion and will be distributed to the participating sites.

The study authorized representative will provide the investigators with a folder/file in which the study-related documents should be archived and maintained. All study documents should be stored in this file by the Investigator. The monitor of the study will regularly check the file to ensure that all relevant documents are maintained. The contents of the folder/file may be subjected to audit/inspection by a designated auditor, regulatory authorities or Hospital Institutional Review Boards (IRBs).

The designated CRO will assure database quality by reviewing the data entered into the CRFs by investigational staff for completeness and accuracy, and in accordance with the data validation plan. The [REDACTED] may perform quality control visits at study sites to ensure implementation of the study protocol and all relevant regulatory and BI procedures.

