## Statistical Analysis Plan

- To assess the patterns of use of afatinib in routine clinical practice in terms of treatment modifications (permanent discontinuations, temporary interruptions, dose changes), and reasons for these modifications.

The secondary endpoints of the study, pertaining to secondary objectives are the following:

- Change in the total LCSS score, ASBI score and individual domain scores from enrolment to each post-baseline predefined timepoints; in addition change throughout the study observation period will be examined using longitudinal analysis;
- Proportion of patients (n, %) with reported problems for each level for each dimension of EQ-5D and proportion of patients with '*no problems*' (i.e., level 1) and '*with problems*' (i.e., level 2 & 3) at enrolment and at the post-baseline predefined timepoints;
- EQ-visual analogue scale (VAS) score (mean  $\pm$  SD) at enrolment and at the post-baseline predefined timepoints;
- Change in the proportion of patients in each of the EQ-5D dimension levels (no problems, with problems) and change in the EQ-VAS score between enrolment and post-baseline predefined timepoints;
- Change in ECOG PS scores from baseline to post-baseline predefined timepoints;
- Ratio of doses actually taken to doses prescribed over the study participation period and reasons for discrepancies;
- Proportions of patients with treatment discontinuations, temporary interruptions, or dose change(s) and reasons for treatment modifications.

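### Adherence is measured only by a diary of missed pills, so on the visible text an unused diary cannot be told from full adherence, and under-recording can only raise the ratio

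*Protocol*

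**What the plan says.** Adherence is a secondary objective (Protocol 10.2): "To record patient adherence to treatment with afatinib during the study observation period as well as the reasons for missing doses". The matching endpoint, worded alike in Protocol 11.1.3.2 and SAP 2.1.2, is "Ratio of doses actually taken to doses prescribed over the study participation period and reasons for discrepancies".

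The data source is stated twice. The abstract has "For the measurement of the adherence to therapy, a patient diary will be used", and Protocol 11.5 says what goes into it: "A patient diary will be used which the patient will be requested to fill in only with the date and reasons for missed pills". Protocol 11.5 defends this choice as light on the patient and as "the most accurate in terms of avoiding recall biases".

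Other exposure data come by a separate route: "All afatinib treatment modifications, concomitant medications, study-related routine clinical assessments, adverse events (AEs) and vital status will also be collected".

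Adherence is also used as a predictor. The logistic model in Protocol 11.8.2 examines baseline characteristics "as well as adherence to therapy at 6 months on the study primary endpoint". Protocol 11.4.4 and SAP 4.1 list adherence, both over 6 months and over the whole participation, among the possible confounders or effect modifiers.

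SAP section 7 refers the adherence analysis to section 8.2, which is not in the public copy. Nor are the Protocol's Table 2 flow chart and the SAP's assessment schedule.

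**The concern.** A record of exceptions works only if silence means that nothing happened. Here silence has two meanings: no dose was missed, or the patient no longer writes. Nothing in the visible text separates them. It mentions no tablet count, no logging of diary return and no statement by the patient that no dose was missed. The completeness review in Protocol 11.5.1 concerns the LCSS and EQ-5D-3L questionnaires. Protocol 11.10 discusses recall in the patient-reported outcomes, not under-recording in the diary. Annex 2 marks the item on validity of exposure measurement as not applicable. SAP 4.2 covers partial dates and the primary endpoint, not blank or unreturned diaries.

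Two results are at stake. One is the descriptive adherence ratio, which would look better than real-world adherence is. The other is the adherence coefficient in the model for symptom improvement. If lapses in writing have nothing to do with symptoms, that coefficient will tend to be diluted. Protocol 9.1 itself links adherence to symptom severity and well-being. If patients who feel worse both miss doses and stop writing, the error is related to the outcome and its direction cannot be foretold.

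**Working it through.** **The plan's own figures.** The documents state no expected adherence, diary-completion rate or precision for adherence, so there is no adherence figure to reproduce. The study-size figures do reproduce (1.96² × 0.25 / 0.10² = 96.04, given as 96; 96 / 0.75 = 128), but they have no bearing here.

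**What the ratio must be.** With only misses written down, the recorded ratio is

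(doses prescribed − misses recorded) / doses prescribed.

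An unused diary has zero recorded misses, so the ratio is 1.00, the same as for a patient who missed nothing.

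**Expected size.** Three quantities are needed, and all are assumptions:
- A: true adherence;
- u: share of missed doses that fall in unused diaries;
- c: share of missed doses written down while the diary is in use.

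Expected recorded ratio = 1 − (1 − A)(1 − u)c.

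Overstatement = (1 − A)[1 − (1 − u)c]. This is never negative. With A below 1, it is zero only if every missed dose is recorded.

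Recorded ratio when diaries in use are complete (c = 1):

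| True A | u = 10% | u = 20% | u = 30% | u = 50% |
|---|---|---|---|---|
| 95% | 95.5% | 96.0% | 96.5% | 97.5% |
| 90% | 91% | 92% | 93% | 95% |
| 80% | 82% | 84% | 86% | 90% |

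With c = 0.7 and u = 20%:
- A = 90%: 1 − 0.10 × 0.80 × 0.7 = 94.4%;
- A = 80%: 1 − 0.20 × 0.80 × 0.7 = 88.8%.

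Extremes over A = 80–95%, u = 10–50% and c = 0.7–1:
- smallest: 0.05 × (1 − 0.90) = 0.5 points;
- largest: 0.20 × (1 − 0.50 × 0.7) = 0.20 × 0.65 = 13 points.

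**An error in the other direction.** Suppose patients also log physician-ordered interruption days as missed, and those days stay in the denominator. Take 6 × 30.5 = 183 days, A = 90%, u = 20%, c = 1 and 7 such days, with the same 80% of them recorded. Recorded misses are 0.80 × (18.3 + 7) = 20.24, and 1 − 20.24/183 = 88.9%, against 92.0% without them. This can be corrected, because interruptions are recorded separately. An unused diary cannot.

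**The case against.** The strongest reply is that the places where a safeguard would be found are not visible: the Table 2 flow chart, SAP 8.2, the eCRF and the diary form itself. Protocol 11.1 also says that some data come from interviewing patients at visits. This stands. A reader might infer that no check exists, and the documents do not support that. But an analysis rule in SAP 8.2 could at most set unreturned diaries to missing. It could not separate a returned blank diary from zero missed doses unless something more is collected.

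A reader might also join the diary to the rule in Protocol 11.9, "For PRO-collected data no queries will be issued", and conclude that a blank diary is never followed up. The only support is that the diary is listed under the patient-reported outcomes in Protocol 11.5. Elsewhere (the abstract, Protocol 11.1.2, SAP 3.3 and 3.7.2) those outcomes are the LCSS and EQ-5D-3L alone, and Protocol 11.5 contrasts the diary with a compliance-specific questionnaire. Even where the rule applies, it governs data queries and does not stop a physician from asking.

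The scope is narrower than it may seem. Interruptions, dose changes and discontinuations are captured separately, and SAP 9.1 subtracts interruptions from exposure, so the gap concerns individual missed pills. The regression in Protocol 11.8.2 uses adherence at 6 months, so lapses later in a participation of up to 48 months affect mainly the descriptive ratio.

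Finally, a diary does limit recall error, as the protocol says. That is a fair reason to keep it, but it does not deal with non-recording.

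**Conclusion.** The point holds as a limitation of the stated collection rule. On the visible text, full adherence and an unused diary give the same data, and under-recording moves the ratio only upward. The direction of that error follows from the documents; its size does not. The 0.5 to 13 points rest wholly on the assumed A, u and c.

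The error carries into the adherence term of the primary-endpoint model. A reader might infer that the primary result is biased too. It is not: the proportion with ASBI improvement does not use adherence. Nor is the net error in the reported ratio certain to be upward, because interruption days logged as misses would pull the other way unless the denominator is adjusted.

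This is a low-cost improvement to a secondary objective and one covariate, subject to what the flow chart, SAP 8.2 and the eCRF already contain.

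**What to change.** First check the flow chart, eCRF and SAP 8.2. Unless already collected, add two items to the eCRF page of each existing visit: *diary returned (yes/no)* and *any afatinib dose missed since last visit, confirmed by the patient (no / yes, number)*. Then state in Protocol 11.5 and the SAP that:
- an interval with neither a returned diary nor a confirmation is scored as missing, not as 100%;
- the ratio is reported with the number of confirmed intervals;
- a sensitivity analysis sets intervals with a returned blank diary and no confirmation to missing.

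No extra visit or test is needed. The cost is two short items and an amendment, which the hospital boards must approve before use (Protocol 11.11.1.1). Data collection began on 01 March 2016, so the items can serve only future visits, and earlier intervals will stay unconfirmed. The confirmation is itself self-report, with recall of about 2 months in the first year and about 6 months after that, so it supplements the diary and does not replace it. Reported adherence may fall slightly.

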### **11.5.1 Administration of patient-reported outcome questionnaires**

For the purposes of the current study, the validated Greek versions of the LCSS and EQ-5D-3L instruments will be administered to the patients via a paper-and-pencil self-administered format.

The questionnaires shall be provided to the patients before completing any other procedures or clinical exam at the study visit. This ensures that the interaction between the respondent and other health care professionals does not influence the patient's responses. The patient will be provided with instructions and a quiet and comfortable place to complete the questionnaires. The respondent should be alone when completing the PROs. Spouses or other accompanying individuals should wait in a separate area during the PROs administration. This minimizes any influence on the respondent's answer and ensures the PROs responses reflect the patient's perspective, and not someone else's.

When the respondent has completed the questionnaires, the study physician shall review them to ensure all questions have been answered. If there are any missing questions, he/she shall point them out to the respondent so they may be completed. However, respondents may omit any question they do not feel comfortable answering.

In order to protect subject confidentiality the name of the patient will not be mentioned on the questionnaires.

### **11.5.2 Data collection schedule and study flow chart**

Being non-interventional and observational in nature, this study does not impose any diagnostic/therapeutic interventions or strict visit schedule. Patients will be treated as per the

routine medical practice in terms of visit frequency, types of assessments performed and with adherence to the local prescribing requirements for afatinib.

[figure not shown]
Upon the enrollment of each patient into the study, the investigator shall follow the below-mentioned procedures:

1. Review of patient's personal medical history, in order to confirm if inclusion/exclusion criteria are met.
2. Explanation of study purpose to the patient and obtainment of signed and dated written ICF, after having provided the required time to the patient to carefully read and understand the information leaflet.
3. Collection of the data from the medical records of the eligible patients, as required by the eCRF as well as completion of the eCRF.

[figure not shown]
Investigators shall record all (S)AEs that are observed by them or reported by the patients. As this is an observational study, patients will continue to be followed by their physicians according to current medical practice and the product's SmPC requirements.

An assessment schedule in tabular format providing information on the recommended data collection schedule that most likely reflects the patterns of routine clinical care of most patients being treated with afatinib is depicted at [Table 2](#).

[figure not shown]
Proprietary confidential information © 2018 Boehringer Ingelheim International GmbH or one or more of its affiliated companies

Proprietary confidential information © 2018 Boehringer Ingelheim International GmbH or one or more of its affiliated companies

Proprietary confidential information © 2018 Boehringer Ingelheim International GmbH or one or more of its affiliated companies

